Investigator overall scoring of treatment side effect severity (one X)									
Absent / Normal Mild Moderate Severe Life-threatening or disabling Death									
Grade 0	Grade 1	Grade 2	Grade 3	Grade 4	Grade 5				

Fig 7. The primary end-point of the study is the investigator's grading of adverse effects following treatment as measured directly after treatment and in all subsequent patient follow-up visits.

According to the defined endpoint, the minimum number of patients must therefore be calculated to support a sufficiently high power for the statement that not more than 30% of patients will experience an overall side-effect of Grade 3 or above based on Common Terminology Criteria for Adverse Events (CTCAE), U.S. Department of health and human services, Ver 5.0, Nov 27, 2017.

Secondary endpoints regarding efficacy, feasibility etc. are also measured and analyzed throughout the study, and form important data for analysis, but are not included in the calculation of the minimum number of patients.

To obtain an initial indication of the necessary number of participants needed in the study, a simple estimation based on the conventional calculation of sample size to estimate a proportion or apparent prevalence with specified precision can be used.

A simple binary outcome is considered:

- Accept: Participants have Grade 2 side effects or lower
- Reject: Participants have Grade 3 side effects or higher

Based on substantial previous clinical experience with the study device (used for other skin treatments), severe side effects and adverse events are very rare, and an estimated proportion of 90% having Grade 2 or lower side-effects is therefore a reasonable starting point for the calculation (P=0.90).

As the measurement of side-effects by the investigator is subjective and with a quite course resolution, a total error can be set to 30% (e = ± 0.15), roughly reflecting the interval between the six possible gradings. A standard confidence interval of 95% can be used (Z = 1.96).

At these inputs, the minimum population for the investigation can be calculated as follows:

$$N = (Z^2 \times P \times (1 - P))/e^2 = (1.96^2 \times 0.90 \times (1 - 0.90)/0.15^2) = 15.37$$

At 16 participants in the study, it is therefore possible to say with 95% confidence that the results of treatments will fall within the acceptable group. The minimum number of participants at various other proportions is shown in Table 2.

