Table 2. Calculated minimum population in an investigation for obtaining statistical significance at a cure rate of p and with a error of $\pm 15\%$

р	0,95	0,90	0,85	0,80	0,75	0,70	0,65	0,60	0,55	0,50
Ν	9	16	22	28	33	36	39	41	43	43

In a second step, power curves can be calculated against an alternative base-line of equal proportions having acceptable and rejectable grades of side-effects (the null hypothesis).

Fig 8. shows the power curve for the study containing the above minimum 16 participants as a function of the actual obtained passed AE-profiles. At the hypothesis of 90% having an acceptable AE-profile after HIFU treatment the power is calculated to be 71%.

Similarly, curves correlating the number of necessary participants at fixed power-levels of 80% and 90% at the hypothesized 90% having an acceptable AE-profile after HIFU treatment can be calculated. As shown in Fig. 9, the study will require 20 participants if a power of 80% is needed, while 26 participants will be needed to reach a power of 90%.

[figure not shown]

Fig. 8. Power curve showing the probability of being able to detect difference between HIFU treatment with 90% passed AE profile against a baseline treatment with 50% acceptable proportion. At the projected succes rate of 90%, the difference in cure rate can be detected with a 95% confidence level and power of above 71% if the population in the investigation is 16 participants.

[figure not shown]

Fig. 9. Power curves showing the necessary population to obtain power levels of 80% and 90%. At the projected acceptable AE-profile of 90%, the hypothesis can be confirmed with a power of 80% probability if the population is 20 participants and a poer of 90% if the population in the investigation is 26 participants.

In conclusion, the statistical analysis shows that participation as low as 16 patients will give an acceptable power, provided the AE profile is in the expected range. At worse AE-profiles, or requirements for a higher power-level in comparison with alternatives, the required population size naturally increases, and populations above 20 will typically needed.

In consideration of the status as an initial tolerability and feasibility study performed on a relatively young population group with low expected drop-out, it is considered that a total of **20 participants distributed among the two centers** will be a well-balanced population taking ethical, clinical and practical issues into due consideration.

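### The 71/80/90% power figures in Section 7 are measured against a 50% baseline, not the 30% Grade 3+ limit, and are not the power of this single-arm study for either comparison

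*Combined protocol and SAP*

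**What the plan says.** Section 5.1 makes tolerability the primary endpoint: the treatment passes if fewer than 30% of treated participants have an overall adverse-event score above Grade 2 at 3 months. It names no test, alpha or confidence level.

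Section 7 (Statistical design and analysis) says "the minimum number of patients must therefore be calculated to support a sufficiently high power for the statement that" no more than 30% of patients will have Grade 3 or above. It then takes two steps.

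- **Precision.** With P = 0.90, e = 0.15 and Z = 1.96 it obtains N = 15.37. It concludes that with 16 participants "it is therefore possible to say with 95% confidence that the results of treatments will fall within the acceptable group".
- **Power.** Here "power curves can be calculated against an alternative base-line of equal proportions having acceptable and rejectable grades of side-effects", and this is labelled the null hypothesis. The Fig. 8 caption describes it as a comparison "against a baseline treatment with 50% acceptable proportion". At 16 participants "the power is calculated to be 71" per cent. For larger samples, "the study will require 20 participants if a power of 80% is needed", and 26 are needed for 90%.

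The section concludes that "participation as low as 16 patients will give an acceptable power" if the adverse-event profile is as expected, and that 20 participants over the two centers "will be a well-balanced population taking ethical, clinical and practical issues into due consideration".

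Sections 5.2 and 6.4 state that the study has no alternative-method arm and no comparator device.

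**The concern.** The claim to be powered sets the acceptable proportion against 70%. The power step sets it against 50%, which appears nowhere in the primary endpoint and is described as if a second treatment were being compared. Showing that more than half of patients do acceptably is a much weaker result than showing that fewer than 30% have Grade 3 or above.

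This is the only power statement for the primary endpoint. The Fig. 9 caption says the hypothesis can be confirmed with 80% power at 20 participants, so an ethics committee or reader is likely to take 80% as the chance of supporting the tolerability claim. The assurance about 16 participants rests on the same figures.

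**Working it through.** **Inputs.** True acceptable proportion 0.90 (Section 7). Null used in the power step 0.50 (Section 7). Null implied by the primary criterion 1 − 0.30 = 0.70 (Sections 5.1 and 7). Confidence 95% (Section 7). One arm, 20 participants in total (Sections 6.4 and 6.5.6). The visible text names neither the power formula nor its sidedness, and Figs 8 and 9 could not be seen, so the source of the plan's figures is inferred.

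**Step 1. Reproduce the plan's figures.** Two independent groups, pooled variance, two-sided 5%, mean proportion (0.9 + 0.5)/2 = 0.7:

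n per group = [1.96·√(2·0.7·0.3) + z·√(0.9·0.1 + 0.5·0.5)]² / 0.4²

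- 80% power (z = 0.8416): (1.2702 + 0.4907)²/0.16 = 19.38, so 20.
- 90% power (z = 1.2816): (1.2702 + 0.7473)²/0.16 = 25.44, so 26.
- Power at 16 per group: Φ[(0.4·√16 − 1.2702)/0.5831] = Φ(0.566) = 71.4%. At 20 and 26 per group it is 81.3% and 90.7%.

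All three stated figures come out, but as sizes **per group** of a two-group trial (40 and 52 in total for 80% and 90%). The unpooled and arcsine versions give 78.3% and 74.6% at 16 per group. If 20 were the total of two groups (10 + 10), power would be 49.6%.

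**Step 2. Single-arm power.** For an exact one-sample binomial test, choose the smallest r with P(X ≥ r | n, p0) ≤ alpha. Power is P(X ≥ r | n, 0.90).

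| n | Stated | vs 50%, one-sided 2.5% | vs 70%, one-sided 5% | vs 70%, one-sided 2.5% |
|---|---|---|---|---|
| 16 | 71% | 93.2% (r = 13) | 51.5% (r = 15) | 18.5% (r = 16) |
| 20 | 80% | 98.9% (r = 15) | 67.7% (r = 18) | 39.2% (r = 19) |
| 26 | 90% | 99.7% (r = 19) | 74.1% (r = 23) | 51.1% (r = 24) |

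At n = 20 against 70%, the attained alpha is 3.5% for r = 18 and 0.8% for r = 19. The normal approximation, Φ[(0.2 − z·√(0.21/20))/√(0.09/20)], gives 68.0% (z = 1.645) and 49.5% (z = 1.96), so discreteness does not explain the gap to 80%.

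Exact power against 70% first reaches 80% at N = 28 (one-sided 5%) or N = 31 (one-sided 2.5%). Because it is saw-toothed, it stays above 80% only from N = 33 or N = 36.

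**Step 3. Does rejecting 50% support the 30% claim?** At n = 20 the test rejects 50% with 15 acceptable, that is, 5 of 20 with Grade 3+. The Clopper–Pearson one-sided 95% upper limit for 5/20 is 45.6%, well above 30%.

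**Step 4. Section 5.1 read as an observed-proportion rule.** Fewer than 30% of 20 means at most 5. P(X ≤ 5) is 98.9%, 80.4% and 41.6% when the true Grade 3+ rate is 10%, 20% and 30%. This does not give 71/80/90% either.

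**Step 5. Effect of the unstated convention.** With 2 of 20 Grade 3+, the exact upper limit is 28.3% (one-sided 95%) or 31.7% (two-sided 95%). The first excludes 30% and the second does not.

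**The case against.** The best defence is that little depends on these figures. This is an initial tolerability and feasibility study, 20 was chosen partly on ethical and practical grounds, and 16 comes first from the precision formula, which reproduces. The 50% null is stated openly, and the arithmetic is right for a two-group comparison. At n = 20 the exact test against 50% and the observed-proportion rule also share one cut-off (at most 5 of 20), so under that reading the wrong null would not change pass or fail.

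Much of this stands. N = 20 does not fall with the figures, and the fault is the choice of null and design rather than a slip in calculation. But disclosing the 50% null does not make it the claim that Section 7 says must be powered. The precision step fixes an interval width, not power against 30%. The shared cut-off shows only that the observed rule is lenient: it passes 41.6% of the time at a true rate of 30%, so it cannot carry a statement made with 95% confidence.

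Section 7 does use Z = 1.96, which points to a two-sided 95% convention, but only for the precision formula; nothing ties it to a test of the 30% limit. The one-sided 5% results are therefore one possible convention, not the plan's own. The unseen figures might name a test, but no single-arm calculation tried gives 71/80/90%.

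**Conclusion.** The concern holds. The stated power is for a comparison with 50% acceptable, while the primary claim needs a comparison with 70%. For this single arm the figures are too low against 50% (about 99% at n = 20) and too high against the 30% Grade 3+ limit (68% or 39% at n = 20, against 80% stated; 51% or 19% at n = 16, against 71% stated).

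These results assume the plan's own 90% true acceptable rate and an exact one-sample binomial test at one-sided 5% or 2.5%; the documents specify neither test nor level. The two-group origin of the figures is an inference, but the verdict does not depend on it. The justification needs correcting; the planned enrolment does not.

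**What to change.** 1. In Sections 5.1 and 7, state the decision rule against the 30% Grade 3+ limit, with the test, alpha and sidedness if a formal test is intended. Settle this before any 3-month data are examined.
2. Remove the 50%-baseline text and the 71/80/90% figures, including those in the captions of Figs 8 and 9.
3. Report the single-arm figure for n = 20 that matches the chosen rule: at most 5 of 20 observed (98.9% pass at a true 10%, 41.6% at a true 30%); exact one-sided 5%, at most 2 of 20 (68% power); or exact one-sided 2.5%, at most 1 of 20 (39% power).
4. Withdraw the statement that 16 participants give acceptable power. Describe the N = 15.37 calculation as a precision calculation only, without the sentence claiming 95% confidence in an acceptable result.
5. Keep N = 20 on the feasibility grounds already given.

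The cost is protocol wording, with no change to enrolment, visits or data collection. The plan would, however, have to show a lower power if a formal test is chosen, or a 41.6% false-pass rate if the observed-proportion rule is kept.

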14.1 Adverse Events

An adverse event (AE) is any untoward medical occurrence, unintended disease or injury or any untoward clinical signs, including an abnormal laboratory finding, in subjects, users or other persons, in the context of a clinical investigation, whether or not related to the investigational device.

14.2 Serious Adverse Events

A serious adverse event (SAE) is any event that led to any of the following:

- a) death,
- b) serious deterioration in the health of the subject, that resulted in any of the following:
 - I. life-threatening illness or injury,
 - II. permanent impairment of a body structure or a body function,
 - III. hospitalization or prolongation of patient hospitalization,
 - IV. medical or surgical intervention to prevent life-threatening illness or injury or permanent impairment to a body structure or a body function,
 - V. chronic disease,
- c) foetal distress, foetal death or a congenital physical or mental impairment or birth defect

14.3 Device deficiency

A device deficient is any inadequacy in the identity, quality, durability, reliability, safety or performance of an investigational device, including malfunction, use errors or inadequacy in information supplied by the manufacturer.

14.4 Reporting to national authorities

The sponsor shall report, without delay to the respective national Medicines Agency all of the following:

a) any SAE that has a causal relationship with the investigational device or the investigation procedure or where such causal relationship is reasonably possible.

- b) any device deficiency that might have led to a SAE if appropriate action had not been taken, intervention had not occurred, or circumstances had been less fortunate.
- c) any new findings in relation to any event referred to in points (a) and (b).

The period for reporting shall take account of the severity of the event. Where necessary to ensure timely reporting, the sponsor may submit an initial report that is incomplete followed up by a complete report.

Analysis of the reporting requirements for AE's and SAE's, i.e. whether reporting should be sent to the respective medical authority, will be conducted as per the guidelines given by the Medical Device Coordination Group (MDCG) in "MDCG 2020-10 Guidance on safety reporting in clinical investigations". Reporting will be done electronically using the templates included in the appendix to this guideline (MDCG 2020-10/2).

Records and reports of events shall include accurate and relevant information on type of event, date, treatment, resolution, assessment of seriousness and relationship to the investigational device and the whole procedure.

The investigational device applies ultrasound generated focused heat to the outer skin, being the mode of action. Unexpected stronger burn than anticipated according to instrument setting is a potential adverse event, which may result in more severe necrosis with delayed wound healing. However, such event is due to the construction of the transducer and the hand piece, and in any case limited to the skin, and therefore primarily a local tolerance issue.

Pain associated with the treatment is foreseeable and an expected adverse event, however, unlikely to be significantly worse than pain associated with other instrumental treatments of skin in general use such as surgical interventions, laser treatment and photodynamic treatment of skin cancer.

The two study centers are hospital departments with immediate access to emergency treatments.

15 Vulnerable population

The study does not include identified vulnerable participants, see inclusion and exclusion criteria.

16 Suspension or premature termination of the clinical investigation

The study is suspended if serious adverse events occur related to the investigational device, and the decision taken by the primary investigator and the sponsor to either terminate the study or continue the study depending of the clarification of the case. Continuation of study may require a protocol amendment.

The study is unblinded and no issue re. premature unblinding is relevant.

Participants having device-related adverse events are followed up upon investigator's discretion with control and medical treatment as required in the individual case.

17 Publication policy

The study will be registered in the European registry (www.clinicaltrials.gov) for ongoing clinical trials.

The result of the study shall be published in a peer-reviewed journal with the consent of all participating investigators, regardless if the overall results of the study is positive or negative.

The research publication shall be submitted to a journal within 6 months after the final study report is available.

18 Bibliography

